3.1 Study Visits

494 Study follow up for participants randomized in the study is (timed from randomization):

496

- 497 • 4-week phone call: 4 weeks \pm 1 week
- 498 • 3-month (on treatment) primary outcome visit: 3 months \pm 2 weeks
- 499 • Parents will be instructed to not patch on the day of the visit

500

3.2 Phone Call at 4-weeks

502 Study personnel will call the parent of each participant 4 weeks \pm 1 week following
503 randomization. The purpose of the call for the patching groups is to determine whether patching
504 is being done, and if so, how it is being done. If patching is not being done correctly, patching
505 instructions will be reviewed with the parents. Parents in the patching groups will be asked if
506 they have had any problems using the ODM. If ODMs have been lost, replacement ODMs may
507 be sent to the parent. Parents in both treatment groups will be asked if they have any questions or
508 concerns about the study.

3.3 Masking Procedures

510 Participants will not be masked to their treatment group, given that they will be asked to patch all
511 waking hours/day (full-time patching group) or not at all (observation group). The investigator
512 treating each participant also will not be masked to treatment group. An examiner masked to
513 treatment group will perform all clinical testing (with the exception of VA testing and
514 administration of questionnaires, which may be performed by unmasked, certified personnel) at
515 the 3-month visit.

3.3.1 Masked Examiner

517 The masked examiner must be a pediatric optometrist, pediatric ophthalmologist, or certified
518 orthoptist who is not aware of the participant's assigned treatment. Because the enrolling
519 investigator will be unmasked to treatment group, they will not be allowed to serve as their own
520 masked examiner.

3.4 Testing Procedures at 3-Month Outcome Visit

522 The following procedures will be performed in the order specified below at the 3-month outcome
523 visit with the participant wearing their current refractive correction (if worn), and without
524 cycloplegia. If unable to complete the entire masked exam during the office visit, the participant
525 can return with 10 days to complete all masked testing (# 6-14 below). Testing procedures #1-5
526 below do not need to be repeated if completed at the initial office visit.

527

528 1. Adherence Monitoring (for patching group):

- 529 • Evaluate compliance by review of study calendar
- 530 • Download adherence data from ODM

531 2. Eye-Related Quality of life: Pediatric Eye Questionnaire (PedEyeQ)

- 532 • Child questionnaire: Completed by children 5 years and older
- 533 • Parent questionnaire: Completed by the parent for all children regardless of age
- 534 (includes parent and proxy questions)

535 3. Symptom Survey:

- 536 • Intermittent Exotropia Symptom Survey completed by children 5 years or older.
- 537 • Single diplopia question to be completed by children 3 or 4 years.
- 538 4. Diplopia Assessment by Parent: Assess diplopia presence and frequency over the last week,
- 539 by parental report. If present, classify diplopia frequency as “2 times or less per day” or
- 540 “more than 2 times per day.”
- 541 5. Monocular Distance VA Testing: Distance VA testing in each eye using the same test
- 542 method used at enrollment.
- 543 6. Stereoacuity Testing (masked): Randot Preschool Stereoacuity at 40 cm.
- 544 7. Control of the Exodeviation #1 (masked):
- 545 • Distance (6 meters)
- 546 • Near (1/3 meter)
- 547 • The same examiner must assess control for all three assessments of control for each visit.
- 548 8. Divergence Amplitude Testing (masked): Measured at distance (6 meters) using a PEDIG-
- 549 approved prism bar as described in the *IXT7 Procedures Manual*
- 550 • Record the break and recovery points
- 551 9. Convergence Amplitude Testing (masked): Measured at distance (6 meters) using a PEDIG-
- 552 approved prism bar as described in the *IXT7 Procedures Manual*
- 553 • Record the blur, break, and recovery points
- 554 10. Control of the Exodeviation #2 (masked) (repeat) (see item #7)
- 555 11. Ocular Alignment Testing (masked):
- 556 • Testing must be performed by a pediatric ophthalmologist, pediatric optometrist, or
- 557 certified orthoptist.
- 558 • Ocular alignment will be assessed by the cover/uncover test, simultaneous prism and
- 559 cover test (SPCT), and prism and alternate cover test (PACT) in primary gaze at
- 560 distance (3 meters) and near (1/3 meter) as described in the *IXT7 Procedures Manual*.
- 561 12. Control of the Exodeviation #3 (masked) (repeat) (see item #7)
- 562 13. Suppression (masked): Assessment at distance using the Office Suppression Test at distance
- 563 (6 meters) as described in the *IXT7 Procedures Manual*
- 564 14. Retinal correspondence (masked): In children aged 6, 7, or 8 years of age at randomization,
- 565 assessment of retinal correspondence will be made using the Hering-Bielschowsky After-
- 566 Image Test as described in the *IXT7 Procedures Manual* using the PEDIG-supplied flash
- 567 unit.

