 117 Score³⁵ at 3 and 6 months (on treatment). Control scores ranged from 0 (phoria) to 6 (constant
 118 exotropia) and were better (lower score) in the patching group at 3 months (distance: 2.3±1.0
 119 points vs 2.7±1.1 points; $P=0.03$; near: 1.2±0.7 points vs 1.5±0.6 points; $P=0.003$), and at 6
 120 months (distance: 2.4±1.1 points vs 2.8±1.2 points; $P=0.03$; near: 1.0±0.6 points vs 1.6±0.9
 121 points; $P=0.003$). Nevertheless, post-treatment outcomes, as well as effects on suppression, angle
 122 of deviation, and fusional amplitudes were not evaluated. In addition, while control improved
 123 with patching, control scores reflect that many participants had persistent intermittent exotropia.

124 PEDIG 2014²² and PEDIG 2015²³: Two PEDIG RCTs evaluated part-time patching (3 hours a
 125 day for 5 months) versus observation in 12- to 35-month-olds²³ and 3- to <11-year-olds²² with
 126 IXT. In published secondary analyses of 6-month outcomes (1-month post cessation of patching

127 treatment), mean control scores and mean angle of deviation were compared between patching
 128 and observation groups. For 12- to 35-month-olds, mean distance control scores were better
 129 (lower) in the patching group compared with the observation group (2.3 points vs 2.8 points;
 130 $P=0.02$) (near control scores were similar: 1.1 points vs 1.4 points; $P=0.26$).²³ In addition, mean
 131 distance angle of deviation (PACT) was significantly smaller in the patched group (24.9 Δ vs
 132 27.9 Δ , $P=0.02$) (near angle was similar: 17.0 Δ vs 19.3 Δ , $P=0.10$). For 3- to <11-year-olds,
 133 distance control scores were similar between groups (2.0 points patching vs 2.3 points
 134 observation; $P=0.094$) but near control scores were lower in the patching group (0.9 points vs 1.2
 135 points; $P=0.013$).²² Mean angle of deviation by PACT was 22.2 Δ in the patching group vs 23.8 Δ
 136 in the observation group ($P=0.012$) at distance and 15.4 Δ vs 17.6 Δ ($P=0.11$) at near.

137 The studies were designed primarily to evaluate deterioration rates, but in post hoc analyses
 138 (publication in process) of 3- to <11-year-olds with a control score of 2 or more at enrollment
 139 and a 3-month on-treatment examination (matching current study inclusion criteria and primary
 140 outcome time-point) distance control improved 0.4 points in the observation group (n=147) and
 141 0.8 points in the patching group (n=125) (mean difference 0.41 points (95% CI, 0.12 to 0.70

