231 IXT is a common eye condition, but long-term surgical treatment outcomes are disappointing,
 232 with high failure rates due to recurrence or undercorrection of the exodeviation. Patching is a
 233 commonly used nonsurgical treatment for which there is some evidence of short-term treatment
 234 benefit (improved exodeviation control and reduced angle of deviation) when prescribed 2-3
 235 hours/day. Nevertheless, the extent to which patching is effective if worn for long periods of
 236 time per day or if any treatment effect is sustained once treatment is discontinued is unknown.

237 Understanding the effectiveness of patching treatment and whether there is a benefit from full-
 238 time patching versus observation alone has important implications for managing children with
 239 IXT. If full-time patching is associated with more improvement in distance control compared to
 240 observation alone, then future studies can be conducted to evaluate different durations of full-
 241 time patching treatment, whether the effect is maintained off-treatment, and how full-time
 242 patching compares to other treatment strategies.

243 In addition, this study would provide evidence of the ability of patching to alter suppression,
 244 anomalous retinal correspondence, and fusional amplitudes, and the relationships of these
 245 clinical characteristics with treatment success, failure, and improvement of IXT. This study
 246 provides an opportunity to explore such relationships, and data are expected to create hypotheses
 247 for future studies.

248 **1.8 Study Objectives**

249 Determine whether full-time patching is more effective than observation for improving distance
 250 control of IXT after 3 months of treatment (on-treatment outcome).

251

252 **1.9 Potential Risks and Benefits of Study Treatment**

253 **1.9.1 Known Potential Risks**

254 There is a risk that patching may create diplopia that then becomes troublesome to the patient,
 255 but this complication is seldom reported. It is possible that some patients will show worsening of
 256 IXT control or increase in magnitude with patching³² or observation,²² but deterioration criteria
 257 will be assessed after 3 months and the short 3-month duration allows for cessation of patching
 258 treatment and/or commencement of other treatment should deterioration of the IXT occur. Skin
 259 irritation may occur. If persistent skin irritation occurs due to the adhesive patch, the participant

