482 Participants randomized to the full-time patching group will patch full-time (all waking hours)
483 for 3 months up until the day before the 3-month primary outcome visit. Daily alternate patching
484 will be prescribed (right eye on even days, left eye on odd days). No other treatment for IXT will
485 be used, except for refractive correction.

486 **2.6 Monitoring of Adherence**

487 Site staff will activate and distribute occlusion dose monitors (ODMs) for participants
488 randomized to patching (patching adherence is not applicable to the observation group).

- 489 • Adherence with patching will be monitored throughout the study by an ODM worn on the
490 inside of the patch for participants randomized to patching.
491 • In addition, parents will be asked to record patching wear time and which eye was
492 patched on a study calendar.

493

Chapter 3: Study Follow-up

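### Masked control testing may slip up to 10 days past the 3-month visit with no word on whether patching continues, so an on-treatment outcome could be scored off treatment

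*Protocol*

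**What the plan says.** Protocol 1.8 sets the objective as distance "control of IXT after 3 months of treatment (on-treatment outcome"), and Protocol 3.1 labels the visit the "3-month (on treatment) primary outcome visit". The title of SAP Section 2 also calls the primary analysis on-treatment.

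Protocol 2.5.2 prescribes full-time patching "for 3 months up until the day before the 3-month primary outcome visit. Daily alternate patching" is then described. Protocol 3.1 adds: "Parents will be instructed to not patch on the day of the visit".

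Protocol 3.4 allows for an exam that cannot be finished. Such a participant "can return with 10 days to complete all masked testing (# 6-14 below). Testing procedures #1-5" need not be done again if they were completed at the first appointment, which 3.4 calls the initial office visit. I read the phrase about 10 days as within 10 days. Items 7, 10 and 12 are the three masked control assessments, so the deferrable block holds the whole primary endpoint. Item 1, which need not be repeated, includes the download of the occlusion dose monitor (ODM).

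Protocol 3.5 bars treatment changes only until the 3-month outcome visit. SAP Section 5 counts expected patching days to the day before that visit. SAP 2.1 and 2.2 have no rule for a visit split over two dates.

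**The concern.** Patching stops by reference to the visit, while the endpoint is measured whenever masked control testing takes place. For most children these fall on the same day. For a child brought back under 3.4 they do not, and nothing says what the family should do in between. By the time anyone knows the exam is incomplete, a family following instructions has already stopped.

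The patching arm could then mix on-treatment and off-treatment scores, with the mix depending on how each site reads the text. The protocol leaves the off-treatment effect to future studies, and Section 1.7 concedes how little is known about it: "if any treatment effect is sustained once treatment is discontinued is unknown". An off-treatment score therefore answers a different question, and no analysis can turn it back into an on-treatment one. Because the ODM need not be downloaded again, the gap might not even be recorded.

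**Working it through.** **1. Timeline on the literal reading.** Call the first appointment day 0 and take the day before as the last patched day.

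- Control tested on day 0: no full unpatched day comes before the test day.
- Control first tested on day 10: days 0 to 9 are unpatched, which is 10 days.
- If patching resumed after day 0, it would cover days 1 to 9, which is 9 days.

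**2. Would the analysis notice?** SAP 2.1 accepts visits from 46 to 137 days after randomization. Taking 3 months as about 91 days, the latest in-window visit plus the latest return is 91 + 14 + 10 = 115 days. That is inside the window, so a return score would be analysed as an ordinary 3-month score. None of the four sensitivity analyses in SAP 2.2 separates such scores.

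**3. Which reading is more natural?**

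- *Patching is over at the first appointment:* 3.4 distinguishes the return from the initial office visit; the ODM download need not be repeated; SAP Section 5 ends expected patching before the visit; the bar in 3.5 lapses at the visit.
- *The visit stays open until masked testing is done:* the flow chart lists the masked control tests as part of the primary outcome visit; 3.4 presents the return as completing that exam; 3.1 alone asks only for a pause on the visit day.

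The first reading fits more of the text, but the documents do not settle it.

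**4. Scope.** A child who finished all three control tests on day 0 and lacks only items 13-14 already has on-treatment control scores. The point concerns children whose control testing itself is deferred.

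**5. Size, as illustration only.** First, the plan's own figure. Inputs from Protocol 7.3: difference 1.15, SD 1.5, correlation 0.30, two-sided 5%, 34 per arm.

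- Residual SD = 1.5 × √(1 − 0.30²) = 1.431
- Standard error = 1.431 × √(2/34) = 0.347
- Noncentrality = 1.15 / 0.347 = 3.31, with 68 − 3 = 65 degrees of freedom
- Power (noncentral t) = 90.4%, in line with the stated 90% at 68 completers; 68 / 0.95 = 71.6, rounded up to 72

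Let f be the share of patched children first tested off treatment and L the share of the effect they have lost. The diluted difference is 1.15 × (1 − fL). **Both f and L are assumed; the documents give neither.**

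| f (children of 34) | L | Difference | Power |
|---|---|---|---|
| any | 0 | 1.150 | 90.4% |
| 5% (about 2) | 25% | 1.136 | 89.7% |
| 10% (about 3) | 25% | 1.121 | 88.9% |
| 10% (about 3) | 50% | 1.092 | 87.3% |
| 20% (about 7) | 50% | 1.035 | 83.6% |
| 20% (about 7) | 100% | 0.920 | 74.3% |

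The last rows need frequent deferral and rapid loss together, and nothing in the documents points to either.

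**6. Direction.** Only the patching arm has a treatment to stop, so a fading effect narrows the difference. If patching has no effect, there is nothing to fade and type I error is unchanged.

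**The case against.** The strongest reply is that this is an ambiguity and not a stop rule shown to be wrong. Section 2.5.2 refers to the primary outcome visit. If that visit is defined by its contents, it is unfinished until control has been tested, 3.5 still bars changes, and patching pauses for a day only. The protocol also sends much of its test conduct to the IXT7 Procedures Manual, which is not among the documents and could hold the missing instruction. Both points stand. They lower the force of the concern but do not remove it, because the protocol leaves treatment status at the primary measurement to site interpretation.

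A second reply is that the effect is negligible: returns may be rare, and 10 days off patching may change nothing. This largely stands too. Protocol 7.3 reports 80% power at a difference of 0.99, and all but the most extreme row of the table stays above that.

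A reader might infer a rate of fade from the earlier part-time patching trial, and the documents do not support this. Protocol 1.3.2 reports, "In published secondary analyses of 6-month outcomes (1-month post cessation of patching" treatment), that in 3- to <11-year-olds "distance control scores were similar between groups (2.0 points patching vs 2.3 points" observation), a gap of 0.3. It also gives a 3-month on-treatment difference of 0.41. The ratio suggests a loss of 1 − 0.3/0.41 = 27%. But the 0.3 compares 6-month scores in the whole cohort, while the 0.41 compares 3-month changes in children with a control score of 2 or more at enrollment. Population, measure and time all differ, so the gap cannot be put down to stopping. With the 0.49 from Protocol 7.3 in place of 0.41, the figure becomes 1 − 0.3/0.49 = 39%. Both also come from 3 hours a day, not full-time patching.

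**Conclusion.** The gap is real. The plan defines an on-treatment outcome, ends patching by the visit, lets the whole endpoint be measured up to 10 days later, and does not say what happens to treatment in between. On the more natural reading, a patched child first tested at the return could be scored after up to 10 unpatched days; on the other reading that does not arise, and sites may differ.

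The size cannot be worked out from the documents. Any bias is toward no difference, does not inflate type I error, and is probably small. It is zero if no child's control testing is deferred or if the effect lasts 10 days. A reader might infer that the primary result is compromised or the trial underpowered. Neither follows: the sample size reproduces, and a material loss of power needs assumptions that the documents do not supply. The case for change rests on keeping the outcome what the protocol says it is, at little cost. It is an optional improvement.

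**What to change.** - In 2.5.2 and 3.4, state that if masked control testing is deferred, the assigned treatment (full-time patching or observation) continues or resumes until the day before the return.
- In 3.5, extend the bar on treatment changes to completion of masked control testing, so that it covers both arms.
- At the return, record the date of masked control testing and download the ODM again.

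The cost is up to about 9 more days of patching for the children concerned, one CRF date, one repeat download at a visit that already takes place, and a short amendment, which under Protocol 9.2 needs IRB approval first. If the Procedures Manual already gives this instruction, the protocol edit only has to repeat it. The useful 10-day return stays, and the sample size and primary model do not change. No added sensitivity analysis is needed.

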3.5 IXT Treatment Changes During Follow-up

569 Changes in treatment are not allowed prior to the 3-month outcome visit.

571 If the participant is experiencing overwhelming social concerns or significant symptoms
 572 associated specifically with IXT, the investigator **must call one of the Protocol Chairs** to
 573 discuss the case and obtain approval for an early 3-month outcome visit (if not already in
 574 window) prior to initiating any non-randomized treatment for IXT.

3.6 Management of Refractive Error During Follow-up

575 Because of the short duration of the study, the spectacles prescribed at randomization may not be
 576 changed or discontinued without contacting a Protocol Chair.
 577

578 In the event that spectacles are lost or damaged after randomization but before the 3-month
579 outcome visit, the spectacles may only be replaced with the same spectacle prescription that was
580 prescribed at randomization.

581

Chapter 4: Testing Procedures and Questionnaires

582 4.1 Clinical Assessments

583 The following test procedures will be completed for all three treatment groups at each visit as
584 defined in the *IXT Procedures Manual*:

- 585 1. Monocular VA Testing: Distance VA will be tested in both eyes with the participant wearing
586 their study-specified spectacle correction. The right eye is tested, with the left eye occluded
587 with an adhesive patch. The left eye is tested after the right eye. Testing must be performed
588 by a certified examiner on a certified VA system (EVA or M&S), using the ATS single
589 surround HOTV for participants 3 to <7 years old and using the E-ETDRS for participants \geq
590 7 years. The same testing method must be used throughout the study. Testing time for both
591 eyes typically is in the range of 5 to 10 minutes.
- 592 2. Randot Preschool Stereoacuity Test: The Randot Preschool Stereoacuity Test measures 6
593 levels (40 to 800 seconds of arc) of stereoacuity at near (40 cm). The test consists of 3
594 booklets, each designed to test 2 levels of stereoacuity, and each level consisting of 4 panels,
595 3 of which contain a random dot stereogram. The participant wears polarized lenses over
596 their spectacle correction. The examiner asks the participant if they can identify a specific
597 black and white shape in the booklet and then asks the participant to point to the panel
598 containing the corresponding stereogram image, as outlined in the *IXT7 Procedures Manual*.
599 The test must be administered by a certified examiner. The certified examiner will be
600 required to be masked to treatment group. Testing time is approximately 2-4 minutes.
- 601 3. Ocular Alignment: Ocular alignment will be assessed by the cover/uncover test, simultaneous
602 prism and cover test when tropia present by cover/uncover test (SPCT), and prism and
603 alternate cover test (PACT), using the PEDIG-approved IXT7 prism bar, in primary gaze at
604 distance (6 meters) and at near (33 cm) as outlined in the *IXT7 Procedures Manual*. The
605 examiner will be required to be masked to treatment group. Testing time is approximately 2-
606 4 minutes.
- 607 4. Cycloplegic Refraction: A cycloplegic refraction will be done prior to enrollment and only if
608 clinically indicated thereafter. After administration of eye drops, it typically takes 30 minutes
609 to achieve cycloplegia, and testing time for refraction of both eyes is in the range of 2 to 10
610 minutes.
- 611 5. Suppression Testing: Suppression will be assessed using the Office Suppression Test which
612 grades the level of suppression while tropic on a 4-level scale. Testing will be performed at 6
613 meters as outlined in the *IXT7 Procedures Manual*. Testing must be performed by a pediatric
614 ophthalmologist, pediatric optometrist, or certified orthoptist. The examiner will be required
615 to be masked to treatment group. Testing time is approximately 3-5 minutes.
- 616 6. Retinal Correspondence Testing: In children 6, 7, or 8 years old at time of randomization,
617 retinal correspondence status will be assessed by the Hering-Bielschowsky after-image test,
618 using a PEDIG-provided flash unit. Correspondence will be assessed when aligned and when
619 tropic to record overall status as either:

620 Testing must be performed by a pediatric ophthalmologist, pediatric optometrist, or certified
 621 orthoptist as outlined in the *IXT7 Procedures Manual*. The examiner will be required to be
 622 masked to treatment group. Testing time is approximately 3-5 minutes.

623

624 7. Control of IXT: Assessment of IXT control will be performed using the Office Control
 625 Scale³⁵ at both distance (6 meters) and near (1/3 meter), fixating an accommodative target.
 626 Testing must be performed by a pediatric ophthalmologist, pediatric optometrist, or certified
 627 orthoptist as outlined in the *IXT7 Procedures Manual*. The examiner will be required to be
 628 masked to treatment group. Testing time is approximately 3-5 minutes.

629 The scale below applies to both distance and near test distance separately.

630 Intermittent Exotropia Control Scale

631 5 = Constant Exotropia

632 4 = Exotropia > 50% of the 30-second period before dissociation

633 3 = Exotropia < 50% of the 30-second period before dissociation

634 2 = No exotropia unless dissociated, recovers in >5 seconds

635 1 = No exotropia unless dissociated, recovers in 1-5 seconds

636 0 = No exotropia unless dissociated, recovers in <1 second (phoria)

637 Not applicable = No exodeviation present

638

639 **Directions:**

640 Step 1: Assessment before any dissociation: Eye alignment is observed for a 30-second period
 641 with distance fixation. The time in seconds that a spontaneous IXT is observed is
 642 counted, and the appropriate control score (3, 4, or 5) is assigned for distance fixation.
 643 This is then repeated for near fixation for another 30-second period; if an exotropia is
 644 observed, then the time in seconds that an eye is observed to be exotropic is counted
 645 and the appropriate score of 3, 4, or 5 is assigned. If a score of ≥ 3 is present, then Step
 646 2 (dissociation) is not required for that test distance. First distance and then near
 647 fixation are assessed before any dissociation (i.e., before step 2).

648 Step 2: Assessment with standardized dissociation is performed only if spontaneous
 649 exotropia is NOT observed during step 1 (control was not a 3, 4, or 5). Instead, control
 650 will be a 0, 1, or 2; this is determined based on the worst score determined from 3
 651 successive 10-second periods of dissociation:

- 652 • An occluder is placed over the right eye for 10 seconds and then removed; the
 653 length of time it takes for the re-establishment of fusion is measured in seconds.
- 654 • The left eye is then occluded for a 10-second period (second assessment under
 655 dissociation) and after uncovering the eye, the time for re-establishment of fusion
 656 is similarly measured in seconds.
- 657 • A third assessment is performed, by covering the eye that required the longer time
 658 to re-fuse on the first two 10-second dissociations. After uncovering the eye, the
 659 length of time (in seconds) it takes for the reestablishment of fusion is measured
 660 in seconds.

661 The worst level of control for the three 10-second periods of dissociation by occlusion
 662 should be recorded.

663 Since the control score is the slowest time of the three assessments, if a score of 2 (>5
664 seconds recovery) is noted on the first or second dissociation, then subsequent
665 dissociation(s) are not needed.

666 If the child has a micro-esotropia by the cover-uncover test but an exodeviation by
667 PACT, the control scale applies to the exodeviation.

668 8. Measurement of Divergence Amplitude: Testing must be performed by a pediatric
